### Predictor 3: stream segregation

A sequence of 6 spoken digits alternating in voice pitch (F0) between a high pitch and a low pitch will be presented. Participants will only repeat digits presented with a high pitch, requiring segregation of the two F0 streams. This is analogous to previous sequential streaming studies which used phonemes (David et al. 2017; Gaudrain et al. 2008), but the use of digits makes identification of individual items easier and insensitive to auditory resolution (Bosen and Luckasen 2019; Moberly, Harris, et al. 2017). Recalling 3 digits from each sequence minimizes variability in recall accuracy which arises at longer list lengths (Unsworth and Engle 2006). The number “seven” will be excluded because it is the only disyllabic digit in English, which can affect recall accuracy (Baddeley, Thomson, and Buchanan 1975; Egner, Sütterlin, and Lugo 2016). The sequence will be presented at a rate of 0.5 s per digit onset. This rate of presentation limits the available strategies to facilitate recall, which avoids introducing variance associated with individual differences in memory strategy (Bailey, Dunlosky, and Kane 2008, 2011). Sequential presentation of digits across streams avoids energetic masking that would arise if streams were presented concurrently. Digits spoken by one talker will be manipulated in Praat to have different F0s, thus keeping vocal tract length constant. Digits will alternate between F0 values of 85/200, 120/200, and 150/200 Hz, with the expectation that recall accuracy will increase as the F0 difference increases because the high and low pitch streams will be more segregated. We will also include a baseline condition in which all digits will be presented with an F0 of 200 Hz and participants recall every other digit, starting with the first. This baseline condition is expected to be more difficult than conditions with alternating voice pitches because no segregation cue is available. The difference in recall accuracy between alternating F0 conditions and the baseline condition will be the metric of stream segregation.

## **Statistical Analysis Plan**

Data analysis will proceed in stages to confirm that our results replicate previous findings with at-home testing and to ensure the assumptions necessary to test for a mediating relationship are met.

### Step 1: Determine the covariance structure of the memory battery

Performance across memory tasks should have a correlation of  $r \approx 0.3$  (Engle et al. 1999; Shipstead et al. 2014), which reflects their common reliance on storage and processing constructs in memory. We will use principal components analysis to examine the loading of task outcomes onto common dimensions. It is possible they will all load onto a single working memory factor (similar to Rönnberg et al. 2016), or they could load onto two orthogonal factors that represent storage and processing (Unsworth and Engle 2007). Principal components with an eigenvalue greater than one will be included in subsequent steps and the remaining components will be discarded as measurement noise.

### Step 2: Predict speech recognition accuracy in quiet

We expect both modulation detection thresholds to be significant predictors of sentence recognition accuracy, which will account for approximately half of the variance. We will compare the likelihood of generalized linear regression models which include only modulation detection thresholds against models which also include the memory components identified in step 1 to determine if these memory components are significant predictors of speech recognition in quiet. We will verify that modulation detection thresholds and working memory task performance are not correlated, as we found in participants with cochlear implants ( $r = -0.36$ ,  $r = -0.15$  for spectral and temporal threshold correlations with digit span,  $p > 0.10$ ).

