## Design

### Sample Size and Power Analysis

Our preliminary data described below indicate that the measures of auditory resolution and working memory we use will correlate with sentence recognition accuracy with coefficients of at least  $r = 0.5$ . Replicating correlations of this magnitude in the proposed study with  $\alpha = 0.05$  and  $\beta = 0.80$  would require 29 participants. We do not currently have an estimate of the indirect path effect sizes in the mediator model because the stream segregation task we are proposing is novel. For a mediator analysis, the needed sample size to achieve  $\beta = 0.80$  is at least 34 participants if the relationship between auditory resolution, working memory and stream segregation and the relationship between stream segregation and speech recognition in noise have effect sizes of 0.59 (Fritz and MacKinnon 2010). Larger sample sizes would be needed for smaller effect sizes. The limited timeline for this project makes it infeasible to power the study for smaller indirect path sizes (e.g. 71 participants if both effect sizes are 0.39), so the goal of this pilot project will be to provide an estimate of the magnitude of these effect sizes as a basis for determining feasibility of subsequent work. The mediator analysis will still be conducted, but interpretation of non-significant outcomes will be framed within the statistical power of the available sample.

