## Participants

30 participants who lost their hearing and received cochlear implants as adults will participate in this study. We will include unilaterally and bilaterally implanted individuals listening with their everyday hearing configuration. Individuals with residual acoustic hearing better than 60 dBA at any audiometric frequency will be excluded to avoid the confounding the study with the effects of bimodal hearing. Participants with residual hearing in the non-implanted ear will inset an earplug into that ear to further ensure the stimuli are inaudible to that ear. The upper age limit on participants will be 80 years of age, to avoid the rising prevalence of dementia at older ages (Piccirillo et al. 2008) while still including a wide age range. We will attempt to recruit equal numbers of men and women, although we will prioritize including all interested participants over achieving parity. All statistical analyses will be conducted with sex as an additional predictor, although we do not expect sex to affect experimental outcomes.

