### Primary Outcome: Speech recognition in two-talker masking speech

Perceptually Robust English Sentence Test Open-set (PRESTO) sentences (Tamati, Gilbert, and Pisoni 2013) will be presented in quiet and with a two-talker masker at an average target-to-masker ratio of +5 dB. Participants will hear lists 7 and 15 in quiet and 13 and 17 in noise, to limit the impact of cross-list differences in difficulty (Faulkner et al. 2015) on speech recognition accuracy. Performance will be quantified as the percentage of keywords correctly identified across sentences (152 keywords per condition).

For the two-talker masker, PRESTO sentences from unused sentence lists will be concatenated into a running speech stream. Two samples of this running stream will be sampled and superimposed to form the competing speech for each target sentence. Two talkers will be used to maximize the impact of informational masking on speech recognition (Freyman, Balakrishnan, and Helfer 2004). The masking speech will start 0.5 s prior to the target speech and stop 0.5 s after to ensure that participants are given a timing cue to distinguish the masker from the target. The combination of target sentence and maskers will be fixed (“frozen”) across participants to account for fluctuations in the amount of energetic masking that arise from interactions between targets and maskers (Buss et al. 2020). We will fix long-term target-to-masker ratio because that is conventional in speech recognition research. In addition, we will calculate short-term envelope ratio, defined as the proportion of time in which the target speech has a larger instantaneous envelope than the masker for each sentence.

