#### Predictor 2: Working memory

Preliminary data in young adults with normal hearing (Bosen and Doria, in review) demonstrate a link between a three different memory tasks and recognition of vocoded speech in the presence of a speech masker. These results indicate that the ability of young adults with normal hearing to recognize vocoded speech in speech is sensitive to individual differences in storage and processing. Digit span is also associated with vocoded sentence recognition in quiet in individuals with normal hearing (Bosen and Barry 2020).

In contrast, we did not find a relationship between PRESTO sentence recognition accuracy in quiet and digit span performance in 20 listeners with cochlear implants after controlling for auditory resolution ( $r = 0.25$ ,  $p = 0.28$ ). This finding differs from results in young adults with normal hearing listening to vocoded speech, but additional working memory tasks are needed to determine the reason for this difference. In this study, we will use a battery of quick, reliable memory tasks which assess both storage and processing to determine their relative importance when listening in quiet and in competing speech. These tasks include the three tasks shown to be associated with vocoded speech recognition in competing speech:

*Reading Span* (primarily processing) – Participants alternate between judging if sentences are semantically sensible and storing letters in memory. Between 3 and 7 sentence-letter pairs are presented in each trial, after which participants recall the letters in order. The outcome is the total percentage of letters recalled in the correct position (Conway et al. 2005).

*Serial Digit Span* (primarily storage) – Participants hear a list of between 2 and 9 spoken digits presented with one second between stimulus onsets, then verbally repeat them in order (Bosen and Barry 2020; Bosen and Luckasen 2019). The outcome is the total percentage of digits recalled in the correct position.

*Free Recall* (primarily storage) – Participants read a list of 12 monosyllabic words shown for 750 ms with 250 ms between words, then repeat back words as they remember in any order. The outcome is the average number of words recalled from the list.

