### Step 3: Test for a mediating relationship of stream segregation for speech recognition in competing speech

We will extrapolate the predictor model for speech recognition in quiet developed in step 2 to the case of speech recognition in competing speech. If the model performs as well for speech in speech as it does for speech in quiet, we would infer that two-talker speech maskers do not introduce meaningful variability into speech recognition outcomes and stop here. If the speech in quiet model is a worse fit, we will add stream segregation to the predictor model and test whether it predicts unique variance in speech recognition accuracy in competing speech. This would demonstrate that stream segregation is a distinct aspect of speech recognition in the presence of competitors. Finally, to complete the mediator analysis we would test whether modulation detection thresholds and memory factors are significant predictors of stream segregation ability.

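### SAP Step 2 tests the memory components by a likelihood comparison in 30 participants without naming family, dispersion or reference distribution; the Gaussian false-positive rate is 5.0% to 9.1% for one or two components, depending on that choice

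*SAP*

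**What the plan says.** SAP Step 2 sets a baseline model with the spectral and temporal modulation thresholds and asks whether memory adds to it: "We will compare the likelihood of generalized linear regression models which include only modulation detection thresholds against models which also include the memory components". The result decides whether the components count as significant predictors. Neither document gives the family, link, dispersion treatment, reference distribution or significance level for this comparison.

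Four other passages fix its ingredients:

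- Protocol, Participants: 30 people, and "All statistical analyses will be conducted with sex as an additional predictor".
- SAP Step 1: "Principal components with an eigenvalue greater than one will be included in subsequent steps". One or two components are foreseen.
- Protocol, Primary Outcome: "Performance will be quantified as the percentage of keywords correctly identified across sentences (152 keywords per condition". Both a Gaussian model for the score and a binomial model for the count are therefore open.
- SAP Step 3, for speech in competing speech: "we will add stream segregation to the predictor model and test whether it predicts unique variance in speech recognition accuracy in competing speech". No test is named there either.

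**The concern.** A likelihood ratio follows chi-square only in large samples. With 30 people and five or six mean parameters, 24 or 25 residual degrees of freedom remain, and the approximation is liberal. If keyword counts are modelled as binomial with dispersion fixed at 1, any listener-to-listener variation that the predictors do not explain is treated as if it were absent, and the error can be much larger.

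Two things are at stake. A memory effect could be called significant at a level looser than the one reported. And because the reference is not fixed, it could be chosen after the data are seen: with two components, any partial R² between 0.181 and 0.221 is significant by likelihood-ratio chi-square and not by F.

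**Working it through.** **The plan's own figure.** Protocol, Sample Size and Power Analysis, gives 29 participants for r = 0.5 at alpha 0.05 and 80% power. Fisher's z, two-sided: ((1.960 + 0.842)/atanh(0.5))² + 3 = 29.01. This agrees. It is the only place where a level is stated, so two-sided 0.05 is carried to Step 2 as an assumption.

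**Inputs.** n = 30 (Participants). Baseline parameters: intercept, two thresholds and sex = 4. Components tested: q = 1 or 2 (SAP Step 1). Residual df = 30 − 4 − q = 25 or 24.

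**Gaussian, maximum-likelihood ratio against chi-square.** LR = n ln(RSS0/RSS1) = 30 ln(1 + qF/df). Rejecting when LR exceeds the chi-square 95% point c is the same event as F > (df/q)(exp(c/30) − 1), so the size is an exact F tail.

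- q = 1: c = 3.841; threshold 25 × 0.1366 = 3.415; P(F(1, 25) > 3.415) = 0.0765.
- q = 2: c = 5.991; threshold 12 × 0.2211 = 2.653; P(F(2, 24) > 2.653) = 0.0910.
- q = 3, with sex: 0.106.
- Without sex (df 26 and 25): 0.071 and 0.082.

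**Gaussian, dispersion estimated on residual df, still against chi-square.** Size = P(F(q, df) > c/q): 0.061 for q = 1 and 0.069 for q = 2.

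**Gaussian, F test.** 0.050 by construction.

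**Smallest effect declared significant (sex included).** One component: partial r = sqrt(1 − exp(−3.841/30)) = 0.347 by likelihood-ratio chi-square, and sqrt(4.242/(4.242 + 25)) = 0.381 by F. Two components: partial R² = 0.181 and 0.221.

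**How many components.** Suppose five tasks are all correlated at 0.3, the value SAP Step 1 expects. Simulated samples of 30 then keep one component in 42.6%, two in 54.8% and three in 2.6%. The average likelihood-ratio size is 0.426 × 0.0765 + 0.548 × 0.0910 + 0.026 × 0.1061 = 0.085.

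**Binomial on 152 keywords, dispersion fixed at 1.** This needs the residual between-person SD on the logit scale, which the documents do not give. Simulation with sex included gives about 5% at SD 0, roughly 7 to 11% at 0.1, roughly a fifth to a quarter at 0.2, and above 40% from 0.4 upward. In simulated keyword data with logit SD 0.4 to 1.0, the F test on percent scores gave 4.1 to 6.2% and the quasi-binomial F test 4.4 to 6.6%.

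**Step 3, only if done by chi-square likelihood ratio.** Adding one term to a model with one or two memory components (df 24 or 23) gives 8.3% or 9.0%.

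**The case against.** The strongest reply is that 7.6% and 9.1% belong to a test the plan never specifies. They need a Gaussian family, a maximum-likelihood variance and a chi-square reference all at once. A reader might infer that Step 2 will run at that level. The documents do not support this: an F test is not excluded, and it holds 5.0%. That part of the objection stands, so the figures are given as conditional.

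A reader might also try to work out the sponsor's habits from the preliminary p-values. Protocol, Predictor 2, reports that "we did not find a relationship between PRESTO sentence recognition accuracy in quiet and digit span performance in 20 listeners with cochlear implants" (r = 0.25, p = 0.28), but with two thresholds controlled for. A partial-correlation t test then has 20 − 4 = 16 df and gives p = 0.31 to 0.33 over the rounding range of r, which does not match 0.28. SAP Step 2 says "We will verify that modulation detection thresholds and working memory task performance are not correlated, as we found in participants with cochlear implants", with r = −0.36 and p > 0.10. If n is 20, r = −0.355 gives 0.125 by t and 0.101 by likelihood-ratio chi-square, so both fit. Neither passage shows which reference Step 2 will use.

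It can also be said that the family is partly indicated. Protocol, Predictor 1, summarises its preliminary generalized linear regression by R² = 0.64 and betas, which suggests regression on scores. It suggests this without stating it. A further inference, that the unscaled binomial error must be very large, fails too: at a small residual SD it is near nominal.

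Finally, this is a pilot: "so the goal of this pilot project will be to provide an estimate of the magnitude of these effect sizes". That limits the consequence. It does not remove the significance decision in Step 2, whose model is then carried into Step 3.

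**Conclusion.** The point holds as a conditional one, and it is minor. Step 2 leaves open choices that put the Gaussian false-positive rate anywhere from 5.0% (F test) through 6.1 or 6.9% (scaled chi-square) to 7.6 or 9.1% (likelihood-ratio chi-square), for one or two components with sex in both models. Three components would give 10.6% on the last route. The unscaled binomial route is unbounded by anything in the documents.

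The figures rest on n = 30, a nominal level of 0.05 taken over from the sample-size section, and normal errors for the Gaussian results. If Step 2's description of the baseline is read as leaving sex out, the likelihood-ratio figures are 7.1 and 8.2%.

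Step 2 concerns speech in quiet, whereas the primary outcome is recognition in two-talker masking speech. Effect estimates under a given model are the same whichever reference is used.

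**What to change.** Add to SAP Step 2: the memory components are tested jointly at alpha 0.05 by an F test with sex in both models, from either linear regression on percent correct or quasi-binomial regression on keyword counts with estimated dispersion; an unscaled chi-square likelihood ratio is not used. The sponsor should name the family before analysis. Add to Step 3 that the unique-variance test of stream segregation uses the same F test if it is done by model comparison.

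The cost is two sentences, with the same data and software. P-values become slightly larger: in the Gaussian model, F-test p = 0.05 corresponds to likelihood-ratio chi-square p = 0.030 (one component) or 0.024 (two). Apparent power falls by 4 to 12 points for partial r from 0.25 to 0.5. From the noncentral F with λ = 30r²/(1 − r²), it goes from 34.5% to 27.5% at r = 0.25 with one component, and from 62.4% to 50.7% at r = 0.4 with two. That loss is only the removal of the inflated level.

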#### Predictor 1: Auditory resolution

Preliminary data from 20 participants with cochlear implants tested in the lab indicates that spectral and temporal modulation detection thresholds predict PRESTO sentence recognition accuracy in quiet. In a generalized linear regression model, spectral and temporal modulation detection thresholds accounted for  $R^2 = 0.64$  of the variance in recognition accuracy (spectral  $\beta = -0.76$ , temporal  $\beta = -0.47$ ). We will repeat these tasks in this study.

Modulation detection thresholds will be measured with a three-interval, three-alternative forced-choice task. The carrier signal is a 60 dB SPL, 400 ms long noise burst with energy between 350 and 6500 Hz (selected to match the stimuli in Litvak et al. 2007), gated on and off with 20 ms  $\sin^2$  ramps. Carriers are modulated in the target interval and was unmodulated in the other two intervals. Feedback is given after each trial. In the temporal modulation detection task, the target interval is sinusoidally amplitude-modulated at a 100 Hz rate, which has been previously shown to correlate with speech recognition in listeners with cochlear implants when presented via direct stimulation (Fu 2002; Luo et al. 2008) and via a loudspeaker (Won et al. 2011). In the spectral modulation detection task, the target interval is spectrally modulated at 0.5 ripples per octave, which has been previously shown to correlate with speech recognition when presented via a loudspeaker (Anderson et al. 2012; Litvak et al. 2007; Saoji et al. 2009). Carrier level for every interval is randomly varied between -3 and +3 dB Sound Pressure Level (SPL) to diminish the availability of loudness differences between modulated and unmodulated intervals (McKay and Henshall 2010).

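### SAP Step 2 treats a non-significant correlation as evidence that modulation thresholds and memory are uncorrelated, which neither the preliminary 20 nor the planned 30 participants can show

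*SAP*

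**What the plan says.** SAP Step 2, on predicting speech recognition in quiet, ends with a planned check: "We will verify that modulation detection thresholds and working memory task performance are not correlated, as we found in participants with cochlear implants". The evidence follows in brackets: r = -0.36 and r = -0.15 "for spectral and temporal threshold correlations with digit span", with p > 0.10. No sample size is given there. The SAP names no test, significance level, interval or limit on |r| for the new data, and it states no consequence if a correlation appears.

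The SAP introduction gives two purposes for the staged analysis. One is to see whether earlier results are reproduced when testing is done at home. The other is "to ensure the assumptions necessary to test for a mediating relationship are met".

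The Protocol supplies the sample sizes. Predictor 1 refers to "Preliminary data from 20 participants with cochlear implants tested in the lab", and Predictor 2 reports on "digit span performance in 20 listeners with cochlear implants after controlling for auditory resolution". For the new study, the Participants section says "30 participants who lost their hearing and received cochlear implants as adults will participate in this study".

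**The concern.** The SAP's only model of two measures being uncorrelated is a p-value above 0.10 in a small sample. Non-significance at that size shows that the data are imprecise, not that the correlation is near zero. Repeating the exercise with 30 participants invites the same mistake.

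The cited value is not small by the SAP's own standard. Step 1 expects correlations of about 0.3 between memory tasks and reads them as a sign of shared constructs, whereas Step 2 takes a magnitude of 0.36 as no correlation.

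The evidence is also narrower than the claim. The preliminary correlations concern digit span alone, while the check covers memory performance generally, which will come from five tasks. Two thresholds and five tasks give up to 2 × 5 = 10 correlations, and nothing says which of them decide the check.

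What is at stake is interpretation. The study asks how auditory resolution and cognition each contribute to speech recognition. A report that the two were verified as uncorrelated would lead readers to treat the contributions as independent when the data could not show it.

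**Working it through.** **Inputs.** Preliminary r = -0.36 and -0.15, p > 0.10 (SAP Step 2). Preliminary n = 20 (Protocol, Predictors 1 and 2; assumed to apply to the SAP Step 2 correlations). Planned n = 30 (Protocol, Participants). Tests are assumed two-sided. Alpha is not stated for this check, so 0.05 (used in the Protocol's sample size section for another purpose) and 0.10 (the marker in SAP Step 2) are both shown.

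**1. Reproduce the plan's figures.** With t = r·√((n-2)/(1-r²)) on n-2 degrees of freedom and n = 20:
- r = -0.36: t = -0.36 × √(18/0.8704) = -1.64, p = 0.119.
- r = -0.15: t = -0.15 × √(18/0.9775) = -0.64, p = 0.53.

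Both agree with p > 0.10. A two-sided p above 0.10 at r = -0.36 needs n of about 21 or fewer, which fits n = 20.

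The Protocol's sample size also reproduces. It assumes that the predictors "will correlate with sentence recognition accuracy with coefficients of at least" 0.5 and says this "would require 29 participants". Reading the stated 0.80 as power, ((1.960 + 0.842)/atanh(0.5))² + 3 = 29.01. That calculation concerns predictors against speech recognition, not predictors against each other.

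**2. What the preliminary data allow.** Fisher z interval: tanh(atanh(r) ± 1.96/√(n-3)), with 1.96/√17 = 0.475.
- r = -0.36: atanh = -0.377, limits -0.852 and 0.098, giving -0.69 to 0.10.
- r = -0.15: atanh = -0.151, limits -0.627 and 0.324, giving -0.56 to 0.31.

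The first interval reaches a correlation that would mean 0.69² = 48% shared variance. It also includes zero.

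**3. How often a real correlation would be non-significant at n = 30.** The critical |r| is 0.361 at the 0.05 level and 0.306 at 0.10. Bivariate-normal simulation (400,000 draws per value, one threshold-memory pair) gives:

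| True correlation | Non-significant, 0.05 rule | Non-significant, 0.10 rule |
|---|---|---|
| 0.30 | 63% | 50% |
| 0.36 | 49% | 36% |

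The Fisher approximation agrees. For 0.30 at the 0.05 level, power is Φ(0.3095 × √27 - 1.96) = Φ(-0.35) = 0.36. For 80% power at the 0.05 level, about 85 participants would be needed at 0.30 and about 59 at 0.36.

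**4. The best case at n = 30.** If the observed r were exactly 0, the 95% interval would be ±tanh(1.96/√27) = ±tanh(0.377) = ±0.36. No result at this size can place the correlation close to zero.

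**5. Effect on the planned models.** With two predictors correlated at 0.36, the variance inflation factor is 1/(1 - 0.36²) = 1/0.8704 = 1.15. This is a minor loss of precision.

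**The case against.** The strongest defence is that little depends on the check. No variable is dropped, no model is chosen and no step is stopped because of it. The Step 2 comparison of thresholds alone against thresholds plus memory components already tests memory conditional on thresholds, and it does not need uncorrelated predictors. This stands. A reader might infer that Step 2 or the mediation analysis is invalid, or that the partial effects would be biased. The planned models do not support that.

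Second, the SAP introduction gives reproduction of earlier results as one purpose, and the check's own wording points to it. A reader might infer that the mediation test rests on this check. The documents do not say so, and mediation with several predictors does not require them to be uncorrelated.

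Third, no decision rule is stated. A reader might infer that r = -0.36 would again pass at n = 30. It would under a 0.05 rule (p = 0.051), but not under the 0.10 marker that the SAP itself uses. The rates above are therefore given for both rules. They apply to one pair; if several true correlations are non-zero, the chance that every pair is non-significant is lower.

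Fourth, a reader might explain the negative sign by audibility of the spoken digits. That is speculation. The Protocol's stream segregation section says that identifying spoken digits does not depend on auditory resolution.

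Finally, the Protocol describes a pilot that aims to estimate effect sizes, and it will read non-significant mediator results in the light of power. That is sound, but the commitment is made for the mediator analysis and not for this check. None of these points makes a p-value above 0.10 evidence of no correlation.

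**Conclusion.** The point holds as a matter of inference and reporting. The statement that no correlation was found is unsupported: the preliminary intervals are -0.69 to 0.10 and -0.56 to 0.31, so the data are inconclusive. Nor do they show that a correlation exists. With 30 participants a true correlation of 0.30 would be non-significant in about 50% to 63% of studies, depending on the rule, and one of 0.36 in about 36% to 49%. Near-independence cannot be shown at this size whatever is observed.

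This rests on n = 20 for the preliminary correlations, two-sided tests, approximate bivariate normality and a single threshold-memory pair. The harm is confined to a possibly false claim that auditory and memory contributions are independent. The planned model comparison is unaffected.

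**What to change.** In SAP Step 2, replace the verification with estimation: the correlations between each modulation threshold and each memory task or retained component will be estimated and reported with 95% confidence intervals. Remove the statement that no correlation was found before. Report the preliminary values as inconclusive, with n and their intervals. Add that a non-significant result will not be taken to show that the measures are uncorrelated. Variance inflation factors for the Step 2 models may be added as an option.

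An equivalence bound such as ±0.3 would not help, because even an observed r of 0 gives an interval of ±0.36 and no result at n = 30 could meet it.

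The cost is a few lines of SAP text and a small table, with no new data and no change in sample size. The downside is that the plan gives up a claim of independence, which 30 participants could not have supported.
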